Various studies have evaluated the outcomes of different barbed suture devices, however there are no reports assessing the length of closure times using STRATAFIX (Ethicon, Johnson and Johnson, Somerville, New Jersey) Knotless Tissue Control Devices during deep closure in total hip arthroplasty. Stephens et al. [5] performed a prospective randomized study of 500 total knee arthroplasty patients who received either barbed suture (250) or conventional sutures (250) for deep closure of the surgical wound. The mean operating time was significantly shorter in the barbed group as compared to conventional group (64.3 vs 68.1 minutes, $p=<0.001$). In a study of 80 TKA (61 barbed, 19 conventional deep sutures) and 54 THA patients (37 barbed, 17 conventional deep sutures), Smith et al. [6] found significantly shorter closure time in the barbed suture group (16.78 vs. 26.5 minutes, $p<0.001$). One study reports one the use of Stratfix suture for intracorporeal suturing in myomectomy. Giampaolino et al. [7] performed a prospective randomized study on 47 patients and evaluated the mean operative time for

laparoscopic posterior myomectomy using Stratafix or conventional suture for intracorporeal suturing. There was a significant decrease in mean operative time associated with use of Stratafix suture as compared to conventional suture (66.3 vs 73 minutes, p=0.005).

This prospective randomized single-center study will examine the outcomes, mainly closure time, of deep closure during total hip arthroplasty using the STRATAFIX Symmetric PDS Plus (Ethicon, Johnson and Johnson, Somerville, New Jersey) barbed suture compared to interrupted VICRYL suture (Ethicon, Johnson and Johnson, Somerville, New Jersey).

Study Design:

In this prospective study examining the deep closure during total hip arthroplasty, active subjects will receive the STRATAFIX Symmetric PDS Plus (Ethicon, Johnson and Johnson, Somerville, New Jersey) suture while the control subjects will receive interrupted VICRYL suture (Ethicon, Johnson and Johnson, Somerville, New Jersey). Superficial closure will be the standard of care for both groups.

The purpose of this study is to compare end points (see below):

- **The primary endpoint** of the study will be closure time and operative time.
- **Secondary endpoints** will examine: wound complications, costs comparison between the two techniques.

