Post-operatively, patients will be assessed at clinic visits at 6 weeks and 3 months. At these time points, we will assess (**Table 1**):

Table 1.

REQUIRED STUDIES	Pre-Op	Intra-operative	6 week post-op	3 month post-op
Informed Consent	x			
Length of surgery time		x		
Length of closure time		x		
Amount of suture material used		x		
Surgeon experience level		x		
Wound complications			x	x

Methods

- A prospective randomized pilot study

Sample

- 60 subjects for a pilot study

Inclusion Criteria:

1. Males and females, between the ages of 18 to 80 years at the time of signing the informed consent document.
2. Understand and voluntarily sign an informed consent document prior to any study-related assessments/procedures are conducted.
3. Able to adhere to the study visit schedule and other protocol requirements.
4. Able to fluently speak and understand the local language
5. If female, is non-pregnant (negative pregnancy test results at the baseline/randomization visit) and non-lactating.
6. End-stage osteoarthritis patients planning to undergo primary total hip arthroplasty
7. BMI less than 40 kg/m²

Exclusion Criteria:

1. BMI greater than or equal to 40 kg/m².
2. History of known bleeding disorder.
3. History of medical co-morbidity that may result in poor wound healing (i.e. diabetes mellitus, peripheral vascular disease).
4. Patients <18 or >80 years of age.
5. Patients who are prisoners.
6. Mentally unable to sign informed consent.
7. Has an uncontrolled illness that, in the opinion of the investigator, is likely to cause the patient to be withdrawn from the trial or would otherwise interfere with interpreting the results of the study.

Screening and Recruitment: Informed Consent

Informed consent will be obtained by one of the study coordinators/co-investigators during a clinical visit prior to procedure in the privacy of an examination room or an office. Patients will be informed about the study and inquired about their interest to participate. A consent document will be given and key parts of the research study will be explained in lay-terms to the patient to ensure full understanding. Any questions regarding the research study

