will be answered at that time. It will be emphasized that participation is voluntary. Those patients who are willing to participate will be asked to sign the consent document along with the consenting researcher. A signed copy of the consent document will be handed to the patient while another copy is kept in their study file.

In the event that an approach prior to the day of surgery is not feasible, same day of procedure consenting will be attempted. Patients will be contacted by telephone (see phone script), and those interested in participating in the study will be informed about what is involved, the follow-up visit, and that participation in the study is strictly voluntary, and will not affect the scheduling of their upcoming surgery. If the patient is interested in participating, the patient can be either mailed or emailed a copy of the informed consent form, and then arrangements will be made to complete the informed consent process prior to the patient being taken back into the preoperative area on the day of surgery. The patient will be asked to come to the hospital on the day of surgery earlier than the time they were told to arrive by surgical scheduling in order to make sure there will be adequate time to discuss the study, including what is involved, risks, benefits, and alternatives. We do not believe that an eventual approach on the same day of procedure would represent an added stress for the patient or delay the start of the procedure. Similar to obtaining informed consent prior to the day of procedure, the process will occur in a private setting with ample time to discuss the study's implications, risks, benefits, and alternatives. No procedures or tests will be conducted on the screening visit after consenting the patient.

Randomization procedures:

Patients will be randomized to either arm of the study as follows: sealed envelopes in a random order will be used to place study participants in either the barbed suture arm or in the traditional suture arm of the study. Patients will be randomized in a one to one ratio. At the commencement of each arthroplasty, a random envelope will be drawn which dictated the type of suture to be used, thus blinding the patients to the type of suture they received.

Research Procedure:

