A standard posterior approach will be performed by the participating surgeons. For the traditional closure (control group), Abductor muscles will be repaired using Ethibond, and the deep fascia will be repaired using interrupted number 1 braided absorbable sutures (Vicryl, Ethicon; Johnson & Johnson, Somerville, NJ). The subcutaneous fat layer will be then closed with simple interrupted knots using number 2-0 braided absorbable sutures (Vicryl), followed by closure of the subcutaneous layer using a number 2-0 monofilament absorbable suture with inverted interrupted knots (Monocryl, Ethicon; Johnson & Johnson) followed by the use of steri-strips and adhesive (See table 2).

For the active arm of the study, wound closure will be performed in this fashion: abductor muscles will be repaired using Ethibond 2-0 (Excel MX69G), and STRATIFIX symmetric PDS Plus #1 will be used to close the fascia. (See Table 2). The subcutaneous fat layer will be then closed with simple interrupted knots using number 2-0 braided absorbable sutures (Vicryl), followed by closure of the subcutaneous layer using a number 2-0 monofilament absorbable suture with inverted interrupted knots (Monocryl, Ethicon; Johnson & Johnson) followed by the use of steri-strips and glue (See table 2).

Closure with the unidirectional barbed suture involves starting at the upper end of the wound and proceeded distally. At the ends of the wounds, the suture is backstitched toward the midpoint for further reinforcement before bringing the needle out through the skin; the suture is then cut flush with the tissue at its free end. With each throw, the leading end of the suture is pulled with only enough tension to engage the barbs with the surrounding tissue, thereby locking the wound edges into approximation. As with the traditional closure and in concordance with our routine protocol, barbed closures were finished with skin steri-strips and adhesive.

Table 2: Suture Type for Closure Following Total Hip Arthroplasty.

Layer	Control Group	Active Group
Muscle	Ethibond 2-0 (Excel MX69G)	Ethibond 2-0 (Excel MX69G)
Fascia	Vicryl #1 (J947H#1)	STRATIFIX (SXPP1A04#1)
Subcutaneous	Vicryl 2.0 (J945H 2-0)	Vicryl 2.0 (J945H 2-0)
Subcuticular	Monocryl 3.0 (Y496H)	Monocryl 3.0 (Y496H)

Skin	Steri-strips, glue (Standard of care)	Steri-strips, glue (Standard of care)
------	---------------------------------------	---------------------------------------

Patient Protection:

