- Cancer: Not related and unexpected within 10 working days from discovery/awareness

b) External Death:

Related/possibly related and unexpected – within 5 working days from discovery/awareness not related whether expected or unexpected – at time of continuing review related/possibly related and expected – at time of continuing review

c) ALL Deaths are also reported at time of continuing review using the AE summary log.

4. Non-serious Adverse events (Internal and External) that are both Related/Possibly related and unexpected are reported on the AE Summary Log at time of continuing review to assess trends.

5. An IRB staff (a qualified, licensed practitioner assigned to this function by the IRB chair and IRB Executive Director) reviews Adverse Event Reports to determine whether they represent Unanticipated Problem Involving Risks to Participants or Others. Events that are assessed, by either the IRB Staff or Investigator, to place subjects or others at a greater risk of harm than was previously known or recognized, or changes the risk/benefit ratio of the study, or

requires a change in the protocol and/or consent document are referred to Full Board for review under Policy #70. Events that do not involve risk to Participants or Others or changes to the informed consent or protocol do not require further review. Investigators are informed of the determination and the IRB file is updated.

6. The AE Summary Log is reviewed by the IRB at the time of continuing review to identify trends in frequency and severity which may impact subject safety.

This study is an Investigator Initiated research trial. Each study site will be considered its own regulatory sponsor and is responsible for internal data monitoring and any study reporting required by ClinicalTrials.gov.

Data Analysis:

Unless otherwise indicated, all testing of statistical significance will be two-sided, and a difference resulting in a p-value of less than or equal to 0.05 will be considered statistically significant. Also, after each analysis, General Linear Models (GLM) will be used to control for possible confounders, including BMI, gender, age and ethnicity.

References:

- [1] A. Sull, S. Inceoglu, A. August, S. Gregorius, and M. D. Wongworawat, “Comparison of Barbed Sutures in Porcine Flexor Tenorrhaphy,” *HAND*, vol. 11, no. 4, pp. 475–478, Dec. 2016.

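### The suture arm is known to the surgical team before closure, and nothing fixes beforehand who closes or how many people suture, so both primary times could reflect personnel as well as suture

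*Combined protocol and SAP*

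**What the plan says.** Under Study Design, the primary endpoint "of the study will be closure time and operative time". Randomization procedures sets when the arm becomes known: "At the commencement of each arthroplasty, a random envelope will be drawn which dictated the type of suture to be used". The same sentence draws one conclusion about masking, "thus blinding the patients to the type of suture they received"; no masking of the surgical team or the timekeeper is stated. Allocation is one to one, with no stratification by surgeon.

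Research Procedure states that "A standard posterior approach will be performed by the participating surgeons". That sentence concerns the approach. The two closures are then described without naming an operator; the barbed closure, for instance, opens with "For the active arm of the study, wound closure will be performed in this fashion". The number of people suturing is not mentioned for either arm.

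Table 1 lists "Surgeon experience level" in the intra-operative column. It does not say whether this means the operating surgeon or the person closing, and it has no row for head count. Data Analysis states that "General Linear Models (GLM) will be used to control for possible confounders, including BMI, gender, age and ethnicity". Surgeon, closer and experience are not among the four named covariates.

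**The concern.** Randomisation protects comparability only for things settled before the arm is known. Patient characteristics are settled by then. The closer need not be: the team knows the suture throughout the operation before closure begins, and can decide afterwards who sutures and whether a second person helps.

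Both primary endpoints are times that depend on the operator. If a less experienced person more often closes in one arm, the difference between arms mixes suture with personnel. Head count raises a similar question in the fascia, where interrupted stitches could be shared between two people more readily than one continuous barbed strand. Extra closing minutes also lengthen the operation, so the same bias can enter both primary endpoints. It would reach the cost comparison too if operating-room time is costed, which the plan does not specify.

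**Working it through.** The only design figure is "60 subjects for a pilot study", which is 30 per arm at one to one. No power, target difference or standard deviation comes with it, so there is no stated calculation to reproduce.

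**Passages side by side**
- Arm known: at the start of the operation (Randomization procedures).
- Closure: at the end of the operation (Research Procedure).
- Rule fixing closer or head count between those points: none found.
- Masking of those who choose the closer: none stated.

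**Reference differences cited in the Background section**
- Operating time, knee arthroplasty: 68.1 − 64.3 = 3.8 min.
- Closure time, mixed series of 80 knees and 54 hips: 26.5 − 16.78 = 9.72 min.

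**Illustrative bias**

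Bias = (difference between arms in the share of cases closed by a slower person) × (extra minutes that person takes). The documents supply neither input. The assumed ranges are 0.20 to 0.40 for the share (for example 6/30 against 12/30, or 6/30 against 18/30) and 3 to 8 min for the extra time.

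- Low: 0.20 × 3 = 0.6 min.
- High: 0.40 × 8 = 3.2 min.

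| Bias | Against 3.8 min | Against 9.72 min |
|---|---|---|
| 0.6 min | 0.6/3.8 = 16% | 0.6/9.72 = 6% |
| 3.2 min | 3.2/3.8 = 84% | 3.2/9.72 = 33% |

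**Effect on the test**

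Take no true suture effect, 30 per arm, two-sided 0.05 and a normal approximation. With residual standard deviation s, extra minutes g and share difference d centred on one half:
- variance v = s² + g²(0.5 + d/2)(0.5 − d/2);
- standard error = √(2v/30);
- false-positive rate = Φ(dg/SE − 1.96) + Φ(−dg/SE − 1.96).

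For d = 0.2, g = 5, s = 4: v = 16 + 25 × 0.24 = 22, SE = √(44/30) = 1.21, bias = 1.0 min, and the rate is 0.131. The values of s are also assumptions.

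| d | g (min) | Bias (min) | s = 4 | s = 6 | s = 8 |
|---|---|---|---|---|---|
| 0.2 | 3 | 0.6 | 0.085 | 0.066 | 0.059 |
| 0.2 | 5 | 1.0 | 0.131 | 0.092 | 0.075 |
| 0.3 | 5 | 1.5 | 0.239 | 0.147 | 0.107 |

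**With the closer declared before the envelope is opened**

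The expected difference in declared closer mix is 0. What remains is chance imbalance, with a standard deviation of √(2 × 0.25/30) = 0.13 in the share difference when half the cases have the slower closer, plus any logged changes. If actual closers match those declared, the test stays at 0.05.

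**The case against.** The strongest reply is that the scenario is conjecture. No passage mentions trainees, handover or two people suturing, and it is natural to read Research Procedure as meaning that the participating surgeons also close. The intra-operative column in Table 1 is a collection window and does not by itself show that experience is recorded after the envelope is opened. Nor does listing the variable show that experience varies much among these surgeons. All of this stands, and it limits the point to what the plan leaves open.

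A second reply is that a safeguard exists: experience is recorded, and the covariate list in Data Analysis is open-ended, so it could be added. That helps an imbalance to be seen. It does not reliably repair one, because a closer chosen after allocation may be a consequence of the arm, and head count is not recorded at all.

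A third is that shared suturing may be part of how the techniques differ in practice, so forcing equal head count would change the question. This is a fair objection to imposing equality. It does not count against declaring the plan beforehand.

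A reader might also infer that head count alone could account for the cited closure-time difference: a 37% saving (1 − 16.78/26.5) from a second person in every control case would remove all 9.72 min. The documents do not support this. Table 2 shows that only the fascial suture differs by arm, and Research Procedure describes interrupted knots above the fascia in both arms, where a second person could help equally. If a second person halved fascial time, the fascia would have to be about 73% of total closure time (0.367/0.5), and no passage says so. The cited series also mixes knees and hips, and the protocol does not say which layers were timed.

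**Conclusion.** The point holds as a gap in design: those who choose the closer can know the arm when they choose, and the plan contains nothing to prevent or reveal a dependence. It would go too far to conclude that closing will differ by arm, that the bias favours one suture, or that the primary comparison is invalid. The documents establish none of these.

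The 0.6 to 3.2 min range rests wholly on the assumed operator effect and share difference, and the cited differences give scale only. Within that range, the bias could be a large part of a difference the size of the cited operating-time result, but no more than about a third of one the size of the cited closure-time result. The change is worth making before enrolment because it is nearly free and later adjustment is a weak substitute.

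**What to change.** In Randomization procedures, require that before the envelope is opened the case sheet records, for each timed layer and not only the fascia:
- the person or persons who will close;
- their experience level;
- the number of people who will suture.

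Define the experience item in Table 1 as that of the declared closer, and show it as recorded before the envelope is drawn. Log any later change of closer or head count with its reason. Report planned and actual closer and head count by arm. In Data Analysis, add a sensitivity analysis that adjusts the general linear model for the declared closer's experience level, which the arm cannot have influenced. Equal head count across arms need not be imposed.

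The cost is a short addition to the protocol, a few case-sheet fields and one extra model, with no added patients or staff. The downside is slightly less freedom to change the closer during a case; necessary changes stay allowed and are logged.

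### Surgeon experience level is a required data item but is not a named covariate in the GLM for closure time or operative time, so some available precision may be lost

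*Combined protocol and SAP*

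**What the plan says.** Under Study Design, the primary endpoint "of the study will be closure time and operative time". Table 1, in the same section, lists "Surgeon experience level" among the required items and marks it in the intra-operative column. The Research Procedure section refers to surgeons in the plural and does not give their number or say who closes. The Sample section gives "60 subjects for a pilot study", with no power, target difference or SD.

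The only statement about adjustment is in Data Analysis: "after each analysis, General Linear Models (GLM) will be used to control for possible confounders, including BMI, gender, age and ethnicity". All four named variables are patient characteristics. Experience has no stated role in the analysis, and Randomization procedures describes no stratification by surgeon or experience.

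**The concern.** Closure time and operative time are task times, so the skill of the person doing the task is a natural candidate to explain part of their spread. The plan collects the one operator variable that could do this and then gives it no use. Whatever variation experience explains beyond BMI, gender, age and ethnicity stays in the residual and widens the interval around the treatment difference. In a trial of 60, that information is worth using if it can be had at almost no cost.

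Three details decide whether it can be used well, and the plan leaves all three open:

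- The levels of experience are not defined.
- It is not said whose experience is recorded.
- The field is intra-operative and the envelope is drawn at the start of the operation, so experience could be recorded, or the closer chosen, after allocation is known. It would then not be a true baseline covariate.

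**Working it through.** **The plan's own figure.** The sample of 60 cannot be reproduced, because no power, difference or SD is given. As a benchmark, 30 per arm at two-sided 0.05 detects (1.960 + 0.842) × √(2/30) = 0.72 SD with 80% power (normal approximation).

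**Inputs from the documents.**
- 60 patients, allocated 1:1, so 30 per arm; two-sided alpha 0.05.
- Operative time: "The mean operating time was significantly shorter in the barbed group as compared to conventional group (64.3 vs 68.1 minutes", a difference of 68.1 − 64.3 = 3.8 min, from a knee study.
- Closure time: "In a study of 80 TKA (61 barbed, 19 conventional deep sutures) and 54 THA patients (37 barbed, 17 conventional deep sutures"; that study "found significantly shorter closure time in the barbed suture group (16.78 vs. 26.5 minutes", a difference of 26.5 − 16.78 = 9.72 min.

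**Assumptions.**
- SD is the residual SD after the four named covariates: 10 min for operative time and 14.8 min for closure time. The second is the largest SD consistent with the cited p < 0.001 if that came from a t-test on all 134 patients: 9.72 / (3.366 × √(1/98 + 1/36)) = 14.8. It is illustrative and does not bound the SD in this trial.
- Partial R² of experience beyond the named covariates is 0.1 or 0.2. It may differ between endpoints.
- Each named covariate uses 1 df, so k = 4 and residual df = 58 − 4 = 54. Experience adds 1 df (two levels, k = 5, df 53) or 2 df (three levels, k = 6, df 52).

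**Formulas.** SE = SD × √(1 − R²) × √(2/30) × √v. Here v = 1 + k/(57 − k) is the expected inflation from chance covariate imbalance: 1.0755 for k = 4, 1.0962 for k = 5 and 1.1176 for k = 6. Power is from the noncentral t with noncentrality difference/SE.

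Worked example, operative time:
- Without experience: SE = 10 × 0.2582 × √1.0755 = 2.678; noncentrality 3.8/2.678 = 1.419; power 28.6%.
- With two levels at R² 0.2: SE = 10 × √0.8 × 0.2582 × √1.0962 = 2.418; noncentrality 1.572; power 33.9%.

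| Endpoint | Without experience | R² 0.1, two levels | R² 0.2, two levels | R² 0, two levels | R² 0, three levels |
|---|---|---|---|---|---|
| Operative, 3.8 min, SD 10 | 28.6% | 30.7% | 33.9% | 28.1% | 27.7% |
| Closure, 9.72 min, SD 14.8 | 67.3% | 71.0% | 76.0% | 66.5% | 65.6% |

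**Break-even.** The SE falls once R² exceeds 1 − 52/53 = 0.02 for one added df, or 1 − 51/53 = 0.04 for two.

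**Interval width.** The 95% half-width is t × SE. Before the inflation term, at R² 0.2 with two levels:
- Operative time: 2.005 × 2.582 = 5.18 min falls to 2.006 × 2.309 = 4.63 min, a gain of about 0.5 min.
- Closure time: 2.005 × 3.821 = 7.66 min falls to 2.006 × 3.418 = 6.86 min, a gain of about 0.8 min.

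Multiplying by √1.0755 before and √1.0962 after gives 5.37 to 4.85 min and 7.95 to 7.18 min, so the gains are almost the same.

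**Sensitivity to SD.** For operative time at an assumed SD of 20, power before inflation goes from 11.2% to 11.9% at R² 0.1 and 12.7% at R² 0.2, which is negligible. For closure time at SD 9.5 (the same back-calculation on the 54 hip patients alone), power before inflation is already 97.3% and rises to 98.4% or 99.2%.

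**The case against.** The strongest reply is that the plan contains no error here. The word *including* leaves the covariate list open, randomisation protects the comparison, and nothing in the documents shows that experience predicts these times. The GLM also runs after another analysis, so a covariate added to it leaves the first test unchanged. The benefit depends on a second change, making the adjusted estimate primary. Finally, this is a pilot with no power target.

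Most of this stands and limits the point. What remains is that an open list is not pre-specification, and that a required field has no stated use. The dependence on which analysis decides is real, so the fix has to cover it. For a pilot, interval width is the better measure than power.

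A reader might infer more than the documents support:

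- *That the result is biased without experience.* The plan's word for its covariates, confounders, invites this, but allocation is randomised. Chance imbalance is possible; systematic bias is not shown.
- *That the plan bars experience from the model.* It does not.
- *That one endpoint suffers more.* The Background puts the emphasis on one of them ("This prospective randomized single-center study will examine the outcomes, mainly closure time, of deep closure during total hip arthroplasty"), but Study Design makes both primary, and which gains more depends on the assumed SDs.
- *That the cited p-values cap the SD here.* They constrain only the cited studies, one in knees and one in mixed knees and hips, and only if they came from t-tests.
- *That experience might explain half the variance.* Nothing in the documents supports so large a share.

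**Conclusion.** The point holds as a minor one. An operator variable that the plan already requires is not pre-specified for two operator-dependent primary endpoints. At a partial R² of 0.1 to 0.2 with two levels, naming it would be worth about 2 to 5 points of power for operative time and 4 to 9 points for closure time at the SDs shown, or at R² 0.2 an interval narrower by roughly 0.5 to 0.8 min on each side. The exposure if experience explains nothing is under 1 point of power with two levels and at most about 1.7 with three.

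These sizes rest on assumed SDs and R² and on differences borrowed from other studies. There is no gain if all cases fall at one level, little for operative time if its SD is large, and none for the main result unless the adjusted GLM is the primary comparison.

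**What to change.** In Data Analysis:

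- Name experience level, in two or three defined levels, as a GLM covariate for both closure time and operative time, alongside the four already listed.
- Use the experience of the planned closer for closure time and of the planned operating surgeon for operative time (one value if they are the same person). Closer experience alone could be the wrong variable for an operation performed by someone else.
- State that the adjusted GLM estimate is the primary comparison for each endpoint.

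On the data sheet, instruct that the field be completed before the envelope is opened.

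The cost is a few sentences, a definition of the levels and one timing instruction. If the closer and the operating surgeon differ, the existing field takes two values. No patients are added, and the statistical price is one or two residual degrees of freedom.
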